2.4. Statistical Hypotheses

No formal hypotheses will be tested for this study given that this is a first time in human study.

3. PLANNED ANALYSES

3.1. Interim Analyses

No formal interim analyses are planned for this study. However, safety, tolerability, and pharmacokinetic data will be reviewed before each dose escalation in Part A (single dose) and Part B (repeat dose), and prior to the investigation of the food effect.

3.2. Final Analyses

The final planned primary analyses will be performed after the completion of the following sequential steps:

- [1] All subjects have completed the study as defined in the protocol.
- [2] All required database cleaning activities have been completed and final database release and database freeze has been declared by Data Management.
- [3] All criteria for unblinding the randomisation codes have been met.
- [4] Randomisation codes have been distributed according to RandAll NG procedures.

4. ANALYSIS POPULATIONS

Population	Definition / Criteria	Endpoint(s) Evaluated
Enrolled Population	
 Defined as all subjects who were enrolled for the trial irrespective of whether they were randomized or not and for whom a record exists on the study database. 	
 Screen Failure
Safety Population	
 Defined as all randomised subjects who receive at least one dose of study medication. If subjects receive a treatment different to their randomised treatment, they will be analysed according to the treatment actually received. 	
 Study Population Safety
Pharmacokinetic (PK) Population	
 Subjects in the Safety population who administered at least one dose of active treatment and have at least one evaluable PK sample. 	
 PK

NOTES :

- Please refer to [Appendix 10](#) which details the population to be used for each display being generated.

4.1. Protocol Deviations

- Important protocol deviations (including deviations related to study inclusion/exclusion criteria, conduct of the trial, patient management or patient assessment) will be summarised and listed.
- Protocol deviations will be tracked by the study team throughout the conduct of the study in accordance with the Protocol Deviation Management Plan.
 - Data will be reviewed prior to unblinding and freezing the database to ensure all important deviations and deviations which may lead to exclusion from the analysis are captured and categorised on the protocol deviations dataset.
 - This dataset will be the basis for the summaries and listings of protocol deviations.
- A separate summary and listing of all inclusion/exclusion criteria deviations will also be provided. This summary will be based on data as recorded on the inclusion/exclusion page of the eCRF.

5. CONSIDERATIONS FOR DATA ANALYSES AND DATA HANDLING CONVENTIONS

Table 1 provides an overview of appendices within the RAP for outlining general considerations for data analyses and data handling conventions.

Table 1 Overview of Appendices

Section	Component
10.1	Appendix 1 : Protocol Deviation Management
10.2	Appendix 2 : Time & Events
10.3	Appendix 3 : Treatment States and Phases
10.4	Appendix 4 : Data Display Standards & Handling Conventions
10.5	Appendix 5 : Derived and Transformed Data
10.6	Appendix 6 : Premature Withdrawals & Handling of Missing Data
10.7	Appendix 7 : Values of Potential Clinical Importance
10.8	Appendix 8 : Model Checking and Diagnostics for Statistical Analyses.
10.9	Appendix 9 : Abbreviations & Trade Marks
10.10	Appendix 10 : List of Data Displays
10.11	Appendix 11 : Example Mock Shells for Data Displays

6. STUDY POPULATION ANALYSES

6.1. Overview of Planned Analyses

The study population displays will be based on the “Safety” population, unless otherwise specified. Outputs will be presented separately for study part A and study part B.

Table 2 provides an overview of the planned study population displays, with full details of data displays being presented in [Appendix 10](#): List of Data Displays.

Table 2 Overview of Planned Study Population Analyses

Display Type	Data Displays Generated	
	Table	Listing
Randomisation		
Planned and Actual Treatment		Y
Subject Disposition		
Subject Disposition	Y	
Reasons for Screening Failures ^[1]	Y	Y
Reasons for Study Treatment Discontinuation	Y	Y
Reasons for Withdrawals	Y	Y
Important Protocol Deviations	Y	Y
Inclusion and Exclusion Criteria Deviations	Y	Y
Demography		
Demographic Characteristics	Y	Y
Race & Racial Combinations	Y	Y
Study Populations	Y	Y
Medical/Surgical History & Concomitant Medications		
Medical/Surgical History		Y
Concomitant Medication	Y	Y
Exposure and Treatment Compliance		
Exposure to Study Treatment	Y	Y
Treatment compliance	Y	Y

NOTES:

- Y = Yes display generated.

1. Conditional displays, if data is available table and listing will be generated.

Categorical variables will be summarized by the number and percentage of subjects, and the continuous parameters will be summarized by n, mean, median, sample standard deviation, minimum and maximum unless otherwise specified.

7. PRIMARY STATISTICAL ANALYSES

7.1. Interim Analyses

No formal interim analyses are planned for this study. However, safety, tolerability, and pharmacokinetic data will be reviewed before each dose escalation in Part A (single dose) and Part B (repeat dose), and prior to the investigation of the food effect.

7.1.1. Overview of Planned Bayesian Dose Escalation Analyses

The Bayesian Dose Escalation analyses will be utilised to guide dose selection after 3 doses in each part of the study. The analyses will be based on the PK population, unless otherwise specified.

During dose escalation, a Bayesian predictive probability of geometric mean $AUC[0-24] > 4.9 \mu\text{g.h/ml}$ and $C_{max} > 0.443 \mu\text{g/ml}$ will be calculated for potential future dose levels and used together with safety and tolerability data to aid next dose selections. The Bayesian predictive probability will be based on Whitehead's method (Whitehead 2001).

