6.3. Planned Dose Escalation and Adjustments

After the initial dose of GSK3036656, the decision to proceed to each subsequent dose level will be made by the Dose Escalation Committee (DEC) based on safety, tolerability and preliminary pharmacokinetic data from the prior lower dose level (Further details regarding dose escalation can be found in the 201040 Dose Escalation Charter). In Part A, safety data for at least 5 days post-dose and PK data for at least 2 days (48 hours) postdose from at least 4 subjects who received active treatment at the prior lower dose level will be reviewed before dose escalation. In Part B, safety data for at least the first 1 week (7 days) of dosing and PK data for at least the first 2 days (48 hours) of dosing from at least 4 subjects who received active treatment at the prior lower dose level will be reviewed before dose escalation. The actual doses to be administered will be selected by the DEC and may involve either an increase or a decrease in the dose, or repeating the same dose.

The exposures (AUC, Cmax) expected with the next selected dose will be predicted by pharmacokinetic assessment and modelling, and by calculating Bayesian predictive probabilities as data permit (more details in Section 10.3.1).

In toxicology studies in dogs, heart valvular and vascular lesions have been observed at relatively high doses and exposures; no such lesions have been seen in rats at similar exposures. To avoid the risk of this adverse event in the FTIH subjects, exposures in the FTIH study will be limited to predefined levels. Based on discussions with the GSK Cardiovascular Safety panel, the study will aim to limit the maximum individual daily plasma AUC(0-24) and Cmax after single or repeat dose to 4.9 µg.h/mL and 0.443 µg/ml, respectively - a 30-fold margin from the corresponding dog NOAEL exposures of 147.0 µg.h/mL and 13.3 µg/ml at which no valvular or vascular lesions have been detected.

Note: The term “mean” applied to group human exposure parameters (e.g., AUC) in this section refers to Geometric Mean of a dose cohort.

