6.3.1. Dose escalation in Part A

In Part A, bigger dose escalation steps may be allowed at lower doses and systemic exposures as the expected risk of adverse events at these exposures is low. At higher doses, smaller dose escalation steps will be used to minimize the risk of adverse events and gastrointestinal intolerance.

The following rules will guide dose selection in Part A:

1. No dose escalation to the next dose will be higher than 6-fold.
2. Once the dose is ≥ 300 mg, any further dose escalation will be no higher than 3-fold irrespective of the observed exposures.
3. The highest dose in Part A will not exceed 1500 mg.
4. A proposed dose will be acceptable if the predicted probability of an individual exceeding a Day 1 plasma AUC (0-24) of 4.9 µg.h/mL or Cmax of 0.443 µg/mL, as estimated by PK modeling and Bayesian analysis (if feasible), is no more than 10%.

5. Based on prior PK data, individual doses may be adjusted, if needed, such that a predicted individual Day 1 AUC (0-24) or Cmax does not exceed 4.9 $\mu\text{g.h/mL}$ or 0.443 $\mu\text{g/mL}$, respectively.

Dosing with food in Part A will be initiated after the exposures achieved with at least two dose levels administered in a fasted state are already known.

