6.3.2. Dose escalation in Part B

Part B may be initiated after the safety and PK data of at least three doses from Part A are already known. The decision to initiate Part B will be made by the GSK Study team in conjunction with the investigator.

The following rules will guide dose selection in Part B:

1. The starting daily dose in Part B will be selected such that its expected exposure (mean AUC[0-24] or Cmax) on the last day of dosing is no higher than the Day 1 exposure of a dose that has been found to be safe and well tolerated in Part A. The expected daily exposures during the dosing period, including on the last day of dosing, will be predicted based on the PK parameters for GSK3036656 established in Part A. As the highest exposure with repeat dosing is expected on the last day of dosing (as a result of accumulation), this approach would select a daily dose which provides systemic concentrations that, at any time during the period of dosing, are not likely to be higher than the ones already found to be safe and well tolerated in Part A.
2. Subsequent doses in Part B may be selected using the criteria described above for the starting dose in Part B. The expected daily exposures during the dosing period, including on the last day of dosing, will be predicted based on available PK data from Part A and from prior cohorts in Part B. Alternatively, a dose may also be selected even if it does not meet these criteria provided it is no more than 4-fold higher than a previous dose that has been found to be safe and well tolerated upon repeat dosing in Part B.
3. The highest daily dose in Part B will not exceed the highest single dose that has been found to be safe and well tolerated in Part A.
4. A proposed dose will be acceptable if the predicted probability of an individual exceeding a daily plasma AUC (0-24) of 4.9 $\mu\text{g.h/mL}$ or Cmax of 0.443 $\mu\text{g/mL}$ on any day of the dosing period, as estimated by PK modeling and Bayesian analysis (if feasible), is no more than 10%.

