10.3.1. Interim Analysis

No formal interim analyses are planned for this study. However, safety, tolerability, and pharmacokinetic data will be reviewed before each dose escalation in Part A (single dose) and Part B (repeat dose), and prior to the investigation of the food effect.

The relationship between dose and plasma GSK3036656 exposure, and associated variability will be characterized by a power model once data are available from 3 dose levels. Prior to that, prediction of the human exposure at the next dose will be based on population PK modelling (if feasible) or on the assumption of dose–exposure proportionality (i.e., doubling the dose gives an approximate doubling of exposure). If prior PK results show less than proportional increase in exposure with increasing dose, the prediction will be based on the assumption that the fold exposure increase to fold dose increase ratio will be the same with the current dose escalation as it was with the previous one. If prior PK results show more than proportional increase in exposure with dose, subsequent dose escalations will not be higher than 3-fold. The power model will be updated as data become available throughout the study. During dose escalation, and once data is available from 3 doses, a Bayesian predictive probability that an individual will have $AUC(0-24)$ greater than 4.9 $\mu\text{g.h/mL}$ or a C_{max} greater than 0.443 $\mu\text{g/mL}$,

will be calculated for the next dose level and used together with safety and tolerability data to aid the next dose selection.

The Bayesian predictive probability will be based on Whitehead's model [[Whitehead, 2001](#)]:

$$\log(y_{ij}) = \theta_1 + \theta_2 \cdot \log(d_{ij}) + \varepsilon_{ij}$$

where

- y_{ij} is the observed or predicted log-AUC variable (AUC[0-24]) or log-Cmax of the j-th dose d_{ij} administered to the i-th subject
- θ_1, θ_2 are population intercept and slope, respectively.
- ε_{ij} is a random error term, with mean zero and variance σ^2 .

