2. SUMMARY OF KEY PROTOCOL INFORMATION

2.1. Changes to the Protocol Defined Statistical Analysis Plan

Any changes from the originally planned statistical analysis specified in the protocol are outlined in below table.

Changes to Protocol Defined Analysis Plan

[figure not shown]
[figure not shown]
Protocol	Reporting & Analysis Plan	
Statistical Analysis Plan	Statistical Analysis Plan	Rationale for Changes

 • Bayesian dose escalation model: $y = \exp(\theta_1 + \varepsilon) \cdot \text{dose}^{\theta_2}$ 	
 • Bayesian dose escalation model: $y = \exp(\theta_1 + r_i + \varepsilon) \cdot \text{dose}^{\theta_2}$ 	
 • An additional random effect (r_i) has been included in the power model for the Bayesian dose escalation analyses in Study Part A to account for the within subject correlation, see Section 7.1.2

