*SAS Version 9.3 or later or R version 3.1.1 or later will be used for the Bayesian analysis, specifying the normal distribution using mean and precision. At least two chains will be run for the estimation of each parameter.

Model Checking & Diagnostics

The posterior distributions of the model parameters will be estimated using the Markov Chain Monte Carlo (MCMC) method.

MCMC chains will be run for as many iterations as needed until convergence is achieved. Convergence will primarily be assessed using trace plots: All chains' trace plots will be inspected visually, to assess the mixing of each chain. Convergence is indicated when all chains appear to be mixing well and overlapping each other randomly (no chain's convergence is indicated until the chains of all model parameters appear well-mixed).

Additional convergence diagnostics, such as Monte Carlo Standard Error divided by the standard deviation of the posterior distribution (MCSE/SD), Gelman-Rubin statistic, effective sample size (ESS) and autocorrelation plots may also be reviewed.

The modelling will be subject to independent quality control, the final results for the probability of exceeding the pre-defined thresholds for both Cmax and AUC[0-24] should have a percentage of difference of $\leq 5\%$ to conclude agreement.

Model Results Presentation

Once the posterior distributions have been estimated, the following inferences and predictions will be estimated using the associated posteriors:

- Predictions of PK parameters AUC[0-24] and Cmax for potential future dose levels: mean, median, 5th and 95th percentiles.
- The Bayesian predictive probability that an individual subject will have AUC[0-24] or Cmax values greater than 4.9 $\mu\text{g.h/mL}$ and 0.443 $\mu\text{g/mL}$ (a 30-fold

Bayesian Statistical Analyses

margin from the dog no observed adverse effect level (NOAEL) exposure), respectively, will be calculated for each potential future dose level in Part 1 and Part 2. Note, prediction in Part 2 will be independent of Part 1.

- Graphical representation of the predictive distribution for AUC[0-24] and Cmax via line plots and density plots.

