7.1.3. Overview of Planned PK Dose Escalation Analyses

Dose escalation for the first 2 dose levels will be based on population PK modelling (if feasible) or on the assumption of dose–exposure proportionality (i.e., doubling the dose gives an approximate doubling of exposure). If prior PK results show less than proportional increase in exposure with increasing dose, the prediction will be based on the assumption that the fold exposure increase to fold dose increase ratio will be the same with the current dose escalation as it was with the previous one. If prior PK results show more than proportional increase in exposure with dose, subsequent dose escalations will not be higher than 3-fold.

The population PK model will be a fit for purpose model. Candidate model selection will be primarily based on a significant reduction in the objective function value (≥ 3.32 , $\chi^2 < 0.05$) and improvement in the fits of diagnostic scatter plots. Inter-individual variability will be modelled using an exponential error model and residual error will be described by a proportional, proportional plus additive, or additive error model, depending on the data. Model performance will be evaluated using a visual predictive check. Simulations for dose recommendations will be conducted to determine the probability of an individual subject exceeding the defined exposure margins for AUC and Cmax.

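### SAP 7.1.1 defines the dose-escalation exceedance probability for the geometric mean, while the protocol's 10% rule and the rest of the SAP define it for an individual subject

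*SAP*

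**What the plan says.** The SAP defines the exceedance probability in three adjacent subsections, and they disagree.

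- SAP 7.1.1: "During dose escalation, a Bayesian predictive probability of geometric mean" AUC[0-24] above 4.9 µg.h/mL and Cmax above 0.443 µg/mL is to be calculated for candidate doses and used to help choose the next one.
- SAP 7.1.2, under the results to be presented: "The Bayesian predictive probability that an individual subject will have AUC[0-24] or Cmax values greater than" the same two limits.
- SAP 7.1.3, for the population PK simulations: "to determine the probability of an individual subject exceeding the defined exposure margins for AUC and Cmax".

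The protocol is consistent.

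- Section 6.3.1 rule 4 (Part A) begins "A proposed dose will be acceptable if the predicted probability of an individual exceeding a Day 1 plasma AUC (0-24", and 6.3.2 rule 4 (Part B) begins "A proposed dose will be acceptable if the predicted probability of an individual exceeding a daily plasma AUC (0-24". Both set a ceiling of 10%.
- Section 10.3.1 plans "a Bayesian predictive probability that an individual will have" an exposure above either limit.
- Section 6.3 notes that a group mean "refers to Geometric Mean of a dose cohort". The Part B starting-dose rule uses a mean in that sense; the 10% rule does not.

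SAP 2.1 lists one change to the Bayesian analysis: a random subject effect "has been included in the power model for the Bayesian dose escalation analyses in Study Part A". It lists no change of target quantity. Shell DE_T2 in SAP Appendix 11 is titled and headed only as a probability of exceeding a threshold, with separate rows for AUC[0-24] and Cmax.

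**The concern.** The protocol protects the individual. The limits are individual maxima, and one subject above either limit stops escalation (protocol 5.5). The 10% ceiling bounds one person's predicted chance of crossing a limit.

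A geometric mean varies less than an individual value. The same 10% applied to it therefore admits higher exposures and no longer bounds the individual risk. The slip would also be hard to see. DE_T2 would look the same under either definition, and the quality-control step in SAP 7.1.2 only checks that two runs agree within 5%. Two programmers who both followed 7.1.1 would agree on the wrong quantity.

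**Working it through.** **The plan's own figures.** The limits are 1/30 of the dog NOAEL exposures (protocol 4.5): 147.0/30 = 4.90 µg.h/mL and 13.3/30 = 0.443 µg/mL. Both reproduce. The documents give no worked exceedance probability, so what follows is an illustration.

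**Inputs**

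- From the protocol: AUC limit 4.9 µg.h/mL; ceiling 10%; 6 actives per Part A period; 50% CV, which protocol 4.5 uses for clearance.
- Assumed: three dose levels at 3-fold spacing, a 2-fold next step, flat priors, and 18 independent observations (16 df).

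**Set-up** (log exposure regressed on log dose)

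- SD = √ln(1 + 0.5²) = 0.472.
- Log doses are 0, 1.099 and 2.197, with mean 1.099, so Sxx = 6 × 2 × 1.099² = 14.48. The next dose is at 2.197 + 0.693 = 2.890.
- Leverage h = 1/18 + (2.890 − 1.099)²/14.48 = 0.277.
- SE of the predicted mean = 0.472 × √0.277 = 0.249.
- The 90th percentile of t with 16 df is 1.337.

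**Highest predicted geometric mean AUC[0-24] that meets 10%:** boundary = 4.9 × exp(−1.337 × √V)

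- Population geometric mean: V = 0.249², boundary 3.51.
- Geometric mean of a future cohort of six: V = 0.249² + 0.472²/6, boundary 3.22.
- Individual: V = 0.249² + 0.472², boundary 2.40.

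**Individual risk at each boundary:** P(t₁₆ > ln(4.9/boundary)/√(0.249² + 0.472²)), where the denominator is 0.534.

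| Quantity held at 10% | Boundary, µg.h/mL | Ratio to individual rule | Individual risk | At least 1 of 6 exceeds |
|---|---|---|---|---|
| Population geometric mean | 3.51 | 1.46 | 27% | 75% |
| Future-cohort geometric mean | 3.22 | 1.34 | 22% | 67% |
| Individual | 2.40 | 1.00 | 10% | 39% |

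The last column averages 1 − (1 − p)⁶ over 2,000,000 posterior draws of mean and SD, because six subjects share the same parameter uncertainty. Treating them as independent would give 85% for the first row and 47% for the third.

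**In reverse:** a dose at exactly 10% on the individual quantity shows about 0.6% on the population geometric mean. The same dose looks very different depending on which number fills the table.

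**Sensitivity**

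- CV cancels from the individual risk, since SE and SD scale together, so 30% and 70% CV also give 27% and 22%. The exposure ratio does change: 1.27 (population) and 1.20 (cohort) at 30% CV, 1.66 and 1.48 at 70%.
- Spacing of 2, 3 or 6-fold and a step of 1.5, 2 or 3-fold: individual risk 21.1% to 30.4% (population), 18.3% to 23.9% (cohort).
- Part A crossover with the random subject effect (9 subjects, each active in 2 of 3 periods, 3-fold spacing, known variances, within-subject correlation 0, 0.5 or 0.8): 24.9% to 32.7% (population), 20.9% to 25.3% (cohort).

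**The case against.** The strongest reply is that SAP 7.1.1 is only an overview. SAP 7.1.2 gives the model, the priors and the list of outputs, and its only exceedance probability is for an individual. The 10% ceiling appears in the protocol alone, in sentences that name an individual. Harm needs two departures: computing the 7.1.1 quantity, and then comparing it with a ceiling written for another one. The 7.1.1 wording may be a drafting remnant. Individual dose adjustment, caps on escalation steps and the one-subject stopping rule also remain, and the dose escalation charter is not available to check.

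Much of this is fair. The excess is conditional, and 7.1.2 is probably the operative text. But 7.1.1 states what will be calculated and what it is for, and nothing ranks 7.1.2 above it. The other controls do not make the 10% comparison correct.

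Three smaller points also stand in part:

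- Joining the limits by 'and' in 7.1.1 but by 'or' in the protocol and 7.1.2 is secondary, because DE_T2 has separate rows.
- The 27% figure reads the geometric mean as a population parameter. The protocol's own note points to the cohort reading, which gives 22%.
- Part A re-doses the same subjects, so their random effects are partly known. Drawing a new subject is the ordinary reading of an individual under this model, but neither document says so.

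**Conclusion.** The concern holds. SAP 7.1.1 contradicts SAP 7.1.2, SAP 7.1.3 and three places in the protocol on the quantity that goes with the 10% ceiling. The change is not declared in SAP 2.1, and DE_T2 does not resolve it.

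If 7.1.1 were followed literally and its result set against 10%, the individual exceedance risk at the boundary would be about 18% to 33% over the settings tried, or 1.8 to 3.3 times the ceiling. Exposure at the boundary would be 1.34 to 1.46 times higher in the 50% CV case. These figures rest on assumed spacing, step size and flat priors, and on a CV that the protocol states for clearance rather than for observed AUC[0-24]. If the 7.1.2 output is used, there is no excess. This should be corrected before the first Bayesian run, because the calculation supports the exposure cap in a first-in-human study.

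**What to change.** 1. Reword the sentence in SAP 7.1.1 so that it matches 7.1.2 and the protocol: for each candidate dose, report the predictive probability that one subject's AUC[0-24] lies above 4.9 µg.h/mL, or that subject's Cmax above 0.443 µg/mL. Say whether the two are reported separately, as the DE_T2 rows imply, or also jointly.
2. State the draw: a new subject from θ₁ + θ₂·log(dose) + rᵢ + ε in Part A, and from θ₁ + θ₂·log(dose) + ε in Part B.
3. Label DE_T2 as the individual-subject predictive probability.

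The cost is a corrected sentence, a line on the draw and a table label. It needs no new data, and no limit, dose, escalation step or model changes.
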